**Table 2. Summary of Study Timeline During the Initial Phase of the Project**

We will continue this study for an additional 5-years that will enroll 350 new patients (in addition to the 280 patients of the initial study) over a 45-month period (~8 patients/month) with the remaining duration of the proposed funding used for patient follow-up testing, data analysis, manuscript preparation, and dissemination of the results. As of June 2016, we have enrolled 280 patients in the first five years and 244 patients in the second five year study. We need approximately 150 patients to complete enrollment.

### ***Patient Randomization***

Patients will be prospectively randomized after anesthesia induction, but before CPB, using a computer generated randomization program into one of two single-blinded groups:

- 1) Blood pressure intervention group (Intervention Group) in which mean arterial pressure during surgery is targeted to be kept above the patient's lower CBF autoregulatory threshold based on continuous monitoring of mean velocity index or cerebral oximetry index (**see CBF Autoregulation Measurements**) or
- 2) Control Group in which mean arterial pressure is maintained during surgery, including CPB, using institutional standard of care.

**Blinding:** Clinicians caring for the patients will participate in managing blood pressure in the Intervention Group and, thus, cannot be blinded. Individuals making the neurologic assessments and performing data analysis will be blinded to the intraoperative management group, providing effective double blinding.

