## **OBJECTIVES:**

The specific aims of this proposal are:

**Aim 1:** To determine whether targeting blood pressure to a level above an individual's lower CBF autoregulatory threshold during CPB (cardiopulmonary bypass) reduces the frequency of the composite end-point of clinical stroke, or a diffusion-weighted MRI brain lesion, or postoperative cognitive decline 4 to 6 weeks after surgery, compared with patients who receive standard empiric blood pressure management. **Hypothesis:** Targeting mean arterial pressure during CPB to a level above an individual's lower autoregulatory threshold reduces the risk for brain injury in patients undergoing cardiac surgery.

**Aim 1a:** To assess whether extracranial and/or intracranial arterial stenosis (detected by MR angiography), or other patient characteristics such as age, gender, hypertension, diabetes, or prior stroke, modify the effect of maintaining blood pressure above an individual's lower CBF autoregulatory threshold on the risk for the above composite neurological outcome. **Hypothesis:** Targeting blood pressure during CPB to a level above an individual's lower autoregulatory threshold reduces the risk for brain injury in patients undergoing cardiac surgery who have extra- and/or intra-cranial arterial stenosis.

**Aim 1b:** To assess whether targeting MAP to a level above an individual's lower CBF autoregulatory threshold during CPB reduces the frequency of cognitive decline 1 year after surgery compared with the use of standard blood pressure management.

**Aim 2:** To compare three methods of continuous monitoring of CBF autoregulation derived from the linear regression correlation between cerebral oximetry O2 saturation and blood pressure (oximetry index), near infrared-derived relative total hemoglobin and blood pressure (hemoglobin volume index), and transcranial Doppler measured CBF velocity and blood pressure (mean velocity index). **Hypothesis:** Mean velocity index, cerebral oximetry index, and hemoglobin volume index provide complimentary data on detecting the lower limit of CBF autoregulation.

Aim 2 has been satisfactorily addressed and will no longer be an aim of this project.

**Aim 3:** To evaluate whether perioperative transcranial Doppler measurements of major cerebral artery blood flow velocity can identify patients prone to the composite neurological end-point. **Hypothesis:** Perioperative transcranial Doppler examination can

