Individualizing blood pressure targets to be above a patient's lower autoregulatory threshold might provide a means to avoid cerebral hypoperfusion during and after CPB. Monitoring of cerebral autoregulation with a moving linear regression correlation coefficient between cerebral perfusion pressure and middle cerebral artery TCD measured blood flow velocity (mean velocity index) has been validated in volunteers and in patients with head trauma, carotid artery stenosis, acute ischemic stroke, and subarachnoid hemorrhage. When autoregulation is lost, flow velocity has a correlation of 1 with cerebral perfusion pressure at low frequencies. This method provides a way to monitor autoregulation continuously at the bedside in contrast to the intermittent ("snap shot") measurements provided by other methods (e.g., PET, inert gas washout). This feature allows for assessment of CBF autoregulation in individual patients rather than estimating a patient's autoregulatory threshold based on summary data obtained from a group of patients. This ability is important in surgical patients, as CBF autoregulation is dynamic and potentially influenced by many perioperative perturbations, including rewarming from hypothermia, volatile anesthetics (dose dependently), and anemia. These methods have been applied in several clinical situations, and measurement of mean velocity index correlated with the degree of carotid artery stenosis and improvement of cerebral dysautoregulation after carotid recanalization.

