### **Drugs/ Substances/ Devices**

- a. The rationale for choosing the drug and dose or for choosing the device to be used. The algorithm for the management of mean arterial pressure during cardiopulmonary bypass as detailed in *Appendix A* which reflects the current standard of care for the institution. The difference between the two randomized groups is when that intervention will take place. For the Control group, the algorithm will be followed as per routine standard of care. For the Blood Pressure Intervention Group, the algorithm will be instituted when the blood pressure is below the lower autoregulatory limits as determined by mean velocity index or cerebral oximetry index.

b. Justification and safety information if FDA approved drugs will be administered for non-FDA approved indications or if doses or routes of administration or participant populations are changed. N/A

c. Justification and safety information if non-FDA approved drugs without an IND will be administered. N/A

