outside the limits of autoregulation,  $M_x$  and  $CO_x$  approach 1, indicating that CBF is blood pressure dependent. Based on our prior studies, we designate the LLA as the highest MAP associated with  $M_x \geq 0.2$  or  $CO_x \geq 0.3$ . These values are within the range found to be associated with poor outcome after traumatic brain injury and adverse outcomes after cardiac surgery. In about 20% of patients, impaired autoregulation is observed when  $M_x$  and  $CO_x$  are  $\geq 0.3$  at all MAPs during CPB (Fig. 6). An attenuated autoregulation plateau is usually observed. Thus, the “optimal” MAP, defined as the MAP with the lowest  $M_x$ , will be the blood pressure target during CPB, as this point is observed in patients with functional and impaired autoregulation. As blood pressure varies during the usual course of surgery, including during the initiation of CPB, no specific interventions are needed to establish autoregulation indices. Clinicians will have access to  $CO_x$  data only for patients randomized to the Intervention Group.

**The autoregulatory threshold will be defined as the mean arterial pressure at which the mean velocity index increases to  $\geq 0.2$  or cerebral oximetry index increases  $\geq 0.3$ .**

Information regarding the mean arterial pressure at which the lower CBF autoregulatory threshold is detected will be made available to the anesthesiologist, perfusionist, and critical care doctors who are caring for the patients in the Intervention Group before and after surgery. Physicians and perfusionists will be told specifically that a patient has been randomized to the Intervention Group and that his/her mean arterial pressure should be kept higher than that value associated with a mean velocity index  $\geq 0.2$  or cerebral oximetry index  $\geq 0.3$ . During surgery, the mean velocity index will be monitored continuously by the investigative team to confirm that treatments are instituted if mean arterial pressure falls below these limits. These same data will be collected in the Control Group but no specific measures for treating blood pressure will be advised.

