### Assessment Schedule

The schemata of study procedures are listed in Table 5.

Assessment Schedule	PRE-OP	DOS before CPB	DOS CPB	DOS after CPB	ICU	POD 1	POD 2	POD 3	POD 4	POD 5-7	4-6 wks POST-OP	1 YEAR POST-OP
Informed consent	X											
Medical history/PE	X											
NIH Stroke Scale	X									X	X	X
Smell Test	X									X	X	
Psychometric and quality of life testing	X									X	X	
Frailty testing	X										X	X
Urine pregnancy test	X											
SAEs/AEs												
Randomization		X										
Mx and CO 2 monitoring		X	X	X								
Bispectral Index Monitoring		X	X	X								
Urine Flow		X	X	X								
Brain MRI										X 1		
MMSE and Abbreviated Digit Span	X											
Delirium assessments						X	X	X	X			
Electrocardiogram	X				X	X	X	X				

**PRE-OP** = preoperatively (up to 2 weeks before surgery); **DOS** = day of surgery; **POD** = postoperative day; **POST-OP** = postoperatively; **SAE** = serious adverse event; **AE** = adverse event; 1 = MRI will be done once between post-op day 3 and post-op day 14; 2 = blood drawn for standard of care ACT measurements that would normally have been discarded will be used for these samples; 3 = a 3mL lavender top vacutainer tube will be drawn in the morning of POD1 at the same time standard of care bloods are drawn; 4 = urine pregnancy test will be done on women of childbearing potential only; 6 = Delirium assessments will be done on 3 of the first 4 postoperative days; 7 = urine flow will be monitored during surgery.

Clinicians caring for the patients will participate in managing blood pressure in the Blood Pressure Intervention Group and, thus, cannot be blinded. Individuals making the neurologic assessments and performing data analysis will be blinded to the intraoperative management group, providing effective double blinding.

Participation in this study will not require discontinuation of a subject's current therapy any more than would be required if the subject were to undergo CABG and/or valve surgery outside of the study. The Control Group will receive standard care practiced here at Northwestern Memorial Hospital. The Blood Pressure Intervention Group will be receiving investigational care. Blood pressure targets during surgery will be at least those of the standard care group or higher based on the individualized autoregulation measurements.

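### Hypotension in the ICU arises after randomization and should not be adjusted for in the treatment-effect model; a minor point is that the period of the individualized pressure limit needs one wording

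*Combined protocol and SAP*

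**What the plan says.** **Adjustment.** Perioperative Blood Pressure Monitoring and Recording has ICU pressure captured every 15 minutes and reviewed daily by study personnel. Hypotensive episodes, defined as MAP below 70 mmHg, are counted so that the primary outcomes can be adjusted for them; the section treats them as a possible confounder. Experimental Problems gives the reason, that postoperative hypotension might itself cause cerebral ischemia, and repeats the intent to adjust without naming an outcome.

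Study Statistics makes the primary analysis an unadjusted two-sided test of proportions. It adds an adjusted relative risk from a Poisson model with robust standard errors. The candidate covariates named there are arterial stenosis on MR angiography, age, gender and baseline risk factors such as hypertension, diabetes and prior stroke. Postoperative hypotension is not named.

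**Period of the limit.** Patient Randomization defines the Intervention Group as one in which "mean arterial pressure during surgery is targeted to be kept above the patient's lower CBF autoregulatory threshold". The paired arm is a "Control Group in which mean arterial pressure is maintained during surgery, including CPB, using institutional standard of care". The text after the Assessment Schedule says "Blood pressure targets during surgery will be at least those of the standard care group or higher based on the individualized autoregulation measurements", and Autoregulation Monitoring says "During surgery, the mean velocity index will be monitored continuously by the investigative team to confirm that treatments are instituted". Other places refer to bypass. The Aim 1 hypothesis is "Targeting mean arterial pressure during CPB to a level above an individual's lower autoregulatory threshold reduces the risk for brain injury". Drugs/ Substances/ Devices describes "The algorithm for the management of mean arterial pressure during cardiopulmonary bypass". In Autoregulation Monitoring the optimal MAP "will be the blood pressure target during CPB". The day-of-surgery procedures text also sets the targets for CPB.

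**The concern.** In a randomized trial a confounder has to precede assignment. Low pressure in the ICU follows both assignment and intervention, and the intervention is itself a way of managing pressure. If the strategy changes ICU hypotension, and ICU hypotension affects the brain, then the episodes lie on the path from treatment to outcome. A model holding them fixed no longer estimates the effect of the assigned strategy. At stake is the adjusted relative risk for the composite of stroke, diffusion-weighted MRI lesion or cognitive decline, which the plan reports beside the unadjusted one.

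The wording of the period matters less, but it determines what the result describes. A team following the arm definition could apply the limit before and after bypass, while the aims would credit the result to pressure during bypass.

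**Working it through.** **1. The plan's own figure.** Inputs from the sample-size text: control risk 0.45; 40% reduction, so 0.45 × (1 − 0.40) = 0.27; two-sided 5%; 80% power.

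- Mean risk = (0.45 + 0.27)/2 = 0.36; difference d = 0.18.
- Uncorrected n = [1.960 × √(2 × 0.36 × 0.64) + 0.842 × √(0.45 × 0.55 + 0.27 × 0.73)]² / 0.18² = (1.330 + 0.561)² / 0.0324 ≈ 110.4, so 111 per arm.
- With continuity correction, n = (110.4/4) × [1 + √(1 + 4/(110.4 × 0.18))]² ≈ 121.3, so 122 per arm. This is the planned figure.
- Power at 122 per arm is 80.2% with the correction and 83.8% without it.

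Neither the ICU covariate nor the period of the limit enters any of these terms.

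**2. Timing.** Randomization takes place after induction of anesthesia and before CPB. The episodes are read from the ICU record, so every one postdates assignment.

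**3. Could treatment affect them?** The plan itself supplies one link: Experimental Problems says postoperative hypotension could injure the brain. The other link, from assignment to ICU hypotension, is plausible but not shown. The arms may differ in intraoperative pressure and vasopressor use. Autoregulation Monitoring also makes the limit available to critical care doctors, without saying whether they should act on it.

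**4. What adjustment would do.** Write the model as log risk = a + b × arm + c × ICU hypotension + baseline terms.

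- If the arm changes ICU hypotension, b leaves out whatever part of the effect runs through it.
- If something else, such as poor cardiac function, drives both ICU hypotension and the outcome, then holding hypotension fixed can unbalance that factor between arms. The direction of the error is then unknown.
- If the arm does not change ICU hypotension, it is balanced in expectation and there is no confounding to remove.

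In none of the three cases is the adjustment needed for a valid comparison of strategies.

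**5. How it could enter.** Study Statistics does not list the covariate, but the monitoring section declares the intent to use it. The Statistical Analysis Plan section looks for confounders among variables that predict the outcome and are unevenly distributed between arms, and does not limit the search to baseline variables. A variable shifted by treatment can meet that criterion because of the shift.

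**6. Period of the limit.** The two wordings are not synonyms, since the Control definition treats surgery as including CPB. The Assessment Schedule has the autoregulation indices monitored before, during and after CPB, so the limit could be used off bypass. Blood Pressure Management gives each arm its own treatment trigger with no time window. Its paragraph on hypotension outside CPB, in the text we have, names no arm and no MAP threshold.

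**The case against.** On adjustment, the primary test and the first-reported relative risk are unadjusted, the covariate is not in the listed model, and only the monitoring section ties it to the primary outcomes. All of that stands, and it limits the damage to the adjusted estimate. It does not remove the stated rule, and the data-driven search for confounders leaves a way in.

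On the period, none of the passages about bypass confines the limit to bypass. The instruction to physicians and perfusionists to keep MAP above the limit has no time window either. The two wordings can be read as an arm summary and its main period. This stands to the extent that the point is one of drafting.

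A reader might go further and infer that the plan fails to define hypotension off CPB, or that the limit is an ICU target. The documents support neither. Appendix A, which holds the treatment protocol, is not shown and may give the off-CPB threshold, so its absence is not a defect. The procedures text sends the limit only to the perfusionist, anesthesiologist and surgeon, and the treatment check operates during surgery. ICU targeting is therefore not established.

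Enrollment is also well advanced. By June 2016, 280 + 244 = 524 patients were in and about 150 remained, so about 524/674 = 78% had been enrolled. A newly imposed period would change the intervention late in the trial.

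**Conclusion.** The adjustment for postoperative hypotension should be dropped from any model of the treatment effect on the primary outcome. This rests on two assumptions: that the episodes to be adjusted for are those read from the ICU record, as the context indicates, and that the assigned strategy may influence them. The first follows the text; the second is a possibility, not a finding. The size of the distortion cannot be estimated, because the documents give neither ICU pressures by arm nor the strength of the link between ICU hypotension and outcome.

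The inconsistent period is a minor clarification. A reader might infer that the trial is confounded, or that its main result is invalid, if the arms also differ off bypass. That does not follow: the randomized comparison validly estimates the strategy as delivered. Only attribution to pressure during CPB would be too narrow, and no off-bypass data by arm are given to show whether it is. The secondary analysis of time below the limit cannot settle this, because it pools the arms and is observational.

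**What to change.** 1. Amend Perioperative Blood Pressure Monitoring and Recording and Experimental Problems so that postoperative hypotension is described by arm and is not entered in the treatment-effect model for the primary outcome. In Study Statistics and the Statistical Analysis Plan section, state that the adjusted relative risk uses baseline characteristics and that this variable is excluded. This needs no new data, no change in sample size and no change to the primary test.

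2. State the period in which the limit was actually used, consistently across Objectives, Patient Randomization, Drugs/ Substances/ Devices, Autoregulation Monitoring, Blood Pressure Management, the procedures text and the repeated aims in Study Statistics. Record existing practice; do not impose a new rule on the remaining patients. Word the aims and conclusion for the strategy as delivered, which may make them broader than CPB.

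3. Tabulate by arm MAP relative to the individual limit and vasopressor use, on CPB and off CPB during surgery. The source data are already recorded: continuous intraoperative pressure, drug doses, and autoregulation data in both arms. One cost should be expected. The planned spreadsheet holds the percentage of time at each pressure and mentions no split by bypass period, so the stored monitoring files may have to be re-extracted. Loss of the Doppler signal off bypass may leave gaps, which the oximetry index should reduce.

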### **Drugs/ Substances/ Devices**

- a. The rationale for choosing the drug and dose or for choosing the device to be used. The algorithm for the management of mean arterial pressure during cardiopulmonary bypass as detailed in *Appendix A* which reflects the current standard of care for the institution. The difference between the two randomized groups is when that intervention will take place. For the Control group, the algorithm will be followed as per routine standard of care. For the Blood Pressure Intervention Group, the algorithm will be instituted when the blood pressure is below the lower autoregulatory limits as determined by mean velocity index or cerebral oximetry index.

b. Justification and safety information if FDA approved drugs will be administered for non-FDA approved indications or if doses or routes of administration or participant populations are changed. N/A

c. Justification and safety information if non-FDA approved drugs without an IND will be administered. N/A

### ***Perioperative Management***

**Preoperative Variables:** Preoperative demographics, medical history (including euroScore calculated based upon the medical history), and medications will be recorded. A history of prior stroke or transient ischemic attack will be made by review of medical records, the results of prior brain imaging studies, or by contacting the patient's primary care physician. Preoperative left ventricular function as assessed by ventriculography or echocardiography will be recorded as normal, mildly depressed (ejection fraction  $\geq 40\%$  but  $< 50\%$ ), moderately depressed (ejection fraction  $\geq 35\%$  but  $< 40\%$ ), or severely depressed (ejection fraction  $< 35\%$ ). The results of carotid artery ultrasound imaging studies obtained before surgery will be recorded.

**Anesthesia and Patient Monitoring:** To avoid hypotension during surgery, patients will not be given angiotensin converting enzyme inhibitors on the day of surgery. The patients will be connected to the NIRS monitor (Invos, Covidien, Boulder, CO) with two self-adhesive probes attached to the forehead, according to manufacturer guidelines. Arterial blood pressure will be measured via a cannula inserted into the radial or femoral artery placed for clinical purposes. Anesthetic drugs will be standardized and will consist of midazolam, propofol, fentanyl, isoflurane, and skeletal muscle relaxants. During CPB, isoflurane will be administered via the membrane oxygenator. Sedation after surgery will be started when sternal wires are placed and will consist of propofol. Propofol will be titrated off when the patient meets institutional standards for tracheal extubation. Postoperative pain will be managed per hospital standard.

A deficiency of current clinical practice is that urine output is measured crudely and intermittently, and it is not precisely recorded. For this study, the patient's urine flow will be measured every 1 min with automatic gravimetric sensing device connected to the urinary catheter collection bag (RenAdapter: Urine Flowmeter and Multiparameter Monitor). The urine bag will hang on the Renalert device intraoperatively to monitor urine output during surgery. At the conclusion of the surgery the device will be removed before the patient is transferred to the intensive care unit.

